8.2. Risk Analysis for the conduct of the clinical investigation

A risk assessment of the clinical investigation will be conducted initially prior to the first subject enrolment and periodically re-assessed based on any new risks identified through the process. This assessment will be completed throughout the duration of the investigation, as defined by the study team.

8.3. Delegation of responsibility

Before initiation of the clinical investigation, sponsor must be provided with key personnel signed and dated curriculum vitae (not more than 2 years old) to verify their qualifications. Key site personnel are those, who treat or evaluate subject data in the clinical investigation. Also, the sponsor will ensure that all site personnel are trained in the investigation procedures, how to complete the CRFs, procedure for reporting an adverse event or serious adverse event (how, when, to whom), and who to contact in case of emergency related to the investigational device.

9. Monitoring

The sponsor is responsible for ensuring appropriate monitoring of the clinical investigation activities. A study-specific monitoring plan has been developed and includes details regarding the monitoring strategy (i.e., on-site, remote, and centralized).

The monitors will be the primary contact for the Principal Investigator and clinical investigation site personnel.

Monitoring activities are mandatory as per good clinical practice; however, the extent and depth of these activities depend on the criticality of the clinical investigation, speed of enrolment, the experience of the clinical investigation site personnel in carrying out clinical investigations and specific study designs.

For this clinical investigation, the below described monitoring procedures have been determined.

The data collected throughout the investigation, and the conduct of the investigation, will be monitored per the monitoring plan to ensure, and verify, that the rights and well-being of the subjects are protected, that the reported data are accurate, complete, and verifiable from source documents, and that the conduct of the investigation complies with the approved CIP, subsequent amendment(s), ISO14155 and the applicable regulatory requirements.

The monitoring will be conducted per the monitoring plan by qualified designee personnel.

The investigator must be available for and agrees to cooperate with Coloplast Clinical Managers (CM) and/or the Clinical Research Associates (CRA) during their visits and ensure that they have direct access to all documents that they require, including direct access to the subjects' files.

The investigation will be subject to internal audits if relevant. All monitoring visits and possible audits will be followed by internal reports and corrective actions, if needed. Follow-up letters will be forwarded to sites after all visits and any findings should be addressed by the investigator or designee.

To ensure proper conduct of the investigation the following visits on site will be performed during the investigation:

- Site selection visit
- Site Initiation Visit
- Periodic Monitoring visits
- Close Out visit

Site selection visit

Depending on the prospective clinical investigation sites experience with the specific investigational device, an on-site qualification or site selection visit shall be performed during which the feasibility of the clinical investigation requirements will be discussed and common agreement between sponsor and principal investigator shall be reached. This visit may also be replaced by one or more phone calls if the principal investigator is known to the sponsor.

Initiation visit

All clinical investigation sites will complete an initiation visit during which full training on all aspects of the clinical investigation will be provided.

Monitoring visit(s)

The site dedicated monitor is to ensure adherence to the clinical investigation plan, the safety of the subjects, accurate data recording on the e-CRFs and to monitor recruitment rates and adherence to follow-up schedules. During the clinical investigation, monitors shall check that appropriate written informed consents have been obtained. The principal investigator shall permit and assist the monitor to carry out verification of completed e-CRFs against data in the source documents.

The principal investigator can delegate tasks to his/her collaborators, however the roles and responsibilities as time period of involvement for each clinical site personnel must be documented on the Site Personnel signature and Delegation list as well as training received before getting involved with the clinical investigation must be documented in the Clinical Investigation Training Log.

The monitor shall inform the sponsor about any problems relating to facilities, technical equipment, or medical staff at the clinical investigation site. The monitor shall also be responsible for notifying such deficiencies in writing to the principal investigator and convene with the clinical investigation site personnel appropriate and timely corrective actions.

The sponsor, or delegate, will provide clinical monitoring, including review of eCRF with verification to the source documentation, as defined in the monitoring plan. The monitor shall make written reports to the sponsor, including documentation of any deviations after each visit and provide written follow up action items if any, to the principal investigator and/or clinical investigation site personnel.

Periodic monitoring visits (remote or on-site) will be performed as soon as reasonable possible, after the site has enrolled the first subject in the investigation. A final monitoring visit will be performed after all subjects on site have completed the investigation.

A remote, centralized review of the data entered in the eCRF, will be performed by Coloplast CM throughout the conduct of the investigation.

9.1. Source data verification

Source data is all information in original records, certified copies of original records of clinical findings, observations, or other activities in the clinical investigation, necessary for the reconstruction and evaluation of the clinical investigation. This includes source data initially recorded in an electronic format.

All documents and data related to the clinical investigation handled by site personnel, shall be produced, and maintained in a way that assures reliability, integrity, control, and traceability, and shall be appropriately stored to provide a complete history.

The Principal Investigator shall assure the accuracy, attribution, completeness, legibility, and timeliness of the data reported to the sponsor in the eCRFs and in all required reports. All printed copies of electronic source documents shall be certified, as indicated by a dated signature by the investigational site personnel at the time the document is printed. Special requirements should be applied to the capture, review, and retention of electronic source data, to ensure reliability, quality, integrity, and traceability.

The data reported in the eCRFs shall be derived from source documents and be consistent with these source documents, and any discrepancies shall be explained in writing. The eCRF can serve as the source document and this must be documented on the Source Data Specification Form. The Source Data Specification Form must be completed at the initiation visit detailing the location of the source data for each data point agreed upon by the Principal investigator.

10. Statistical considerations

10.0. Statistical design, method, and analytical procedures

The primary objective will be evaluated by analysis of the primary endpoint [REDACTED]

[REDACTED]. The secondary objective will be evaluated by analysis of the secondary endpoints.

All baseline measurements, endpoints and assessments will be summarized by descriptive statistics and/or listed. Endpoints and assessments will be summarized by product. Descriptive statistics for continuous variables are presented with N, Mean, SD (standard deviation), Median, Min and Max, where N denotes the number of subjects contributing with non-missing data. For discrete variables, descriptive statistics are presented with N and percentage, where percentage is based on the total number of subjects/observations with non-missing data.

Other summaries can be made, if relevant. As it is an exploratory study no adjustment for multiple testing will be applied.

All statistical analysis and summaries will be performed with SAS (version 9.4/Enterprise Guide version 7.1)

Definition of analysis populations

Intention to Treat (ITT) and Safety populations will be defined at a formal data review meeting before database lock. As a minimum, the data manager, the clinical manager, and the statistician will be involved in the classification of subjects.

The ITT population (full analysis set) will be constituted by all included subjects with valid informed consent who have been exposed to at least one product, with information on at least one product with respect to the primary endpoint or the secondary endpoints.

Any exclusion of subjects from the ITT population must be documented. Invalid individual data points may be omitted from analysis even though the corresponding subject is part of the ITT population. Any exclusion of data points will be documented.

The Safety population will be constituted by subjects who have given informed consent.

All statistical analysis will be based upon the ITT population whereas adverse events and device deficiencies will be assessed based on the safety population.

Considering the data obtained it might be considered to make additional explorative analyses based on a subset of the ITT population.

Analysis of the primary endpoint

The leakage (Y/N) per bag change will be analyzed by a repeated logistic regression model. The model will consider that observations corresponding to different subjects are independent, whereas observations corresponding to the same subject are correlated. The correlation between observations corresponding to the same product can be larger than observations corresponding to different products. Hence the model includes a fixed effect of product (SenSura Mio, test product), a fixed period effect, a random effect of subject and a random interaction effect of product and subject.

The marginal proportion of leakage for two products will be estimated and it will be tested if the odds ratio is significantly different from 1 on a 5% test level.

Analysis of the secondary endpoints

For preference, where the possible answer is "Yes" or "No", the proportion of subjects answering "Yes" will be calculated. By use of an exact test in the Binomial distribution a 95% confidence interval will be estimated for the proportion. Further, it will be tested if the proportion is significantly different from 50% when using a 5% test level. For questions answered on a 4-point scale the answers will be grouped in 2 (e.g., "Very satisfied" or "Satisfied", represented by "Yes" against "Very dissatisfied" and "Dissatisfied" represented by "No") and analysed using the method described above.

Analysis of the exploratory endpoint

[REDACTED]

[REDACTED]

[REDACTED]

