10.1. Sample size

The primary objective is to investigate the performance of a new 2p coupling in comparison with the SenSura Mio Click coupling with regards to leakage at the coupling during wear in a clinical setting. This will be done by testing if the odds ratio for the estimated proportions of leakage with the two products is equal to one.

[REDACTED]

[REDACTED]

[REDACTED]

[REDACTED]

Drop-out subjects will not be replaced but to account for an assumed drop-out rate of 20%, 50 subjects will be randomized in the study.

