10.2. Level of significance and power

A two-sided significant level of 5% will be applied. For a description of the power see section 10.2 above

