10.3. Pass/fail criteria

The purpose of the investigation is fulfilled:

- if the estimated proportion of leakage from the new coupling system is not statistically significant different from the current SenSura Mio 2p Click solution,
- or the estimated difference is not clinically relevant worse.

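### Does a random-effects logistic model conflict with the promise of marginal leakage proportions and their odds ratio?

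*Combined protocol and SAP*

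**What the plan says.** Section 10.0 (analysis of the primary endpoint) states: "The leakage (Y/N) per bag change will be analyzed by a repeated logistic regression model". It specifies that "the model includes a fixed effect of product (SenSura Mio, test product), a fixed period effect", together with "a random effect of subject and a random interaction effect of product and subject". It then promises two outputs. The first is "The marginal proportion of leakage for two products will be estimated". The second is a test: "it will be tested if the odds ratio is significantly different from 1 on a 5% test level".

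Section 10.1 describes the same test as "testing if the odds ratio for the estimated proportions of leakage with the two products is equal to one". Section 10.2 adds: "A two-sided significant level of 5% will be applied".

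Section 10.3 counts the purpose as fulfilled in either of two ways: the leakage proportions do not differ significantly, "or the estimated difference is not clinically relevant worse". The second route states neither a scale nor a numeric limit.

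Earlier in section 10.0, endpoints are to be summarised by product, with counts and percentages for discrete variables based on non-missing data.

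The visible text does not say how marginal proportions come out of the random-effects model, or whether the odds ratio is conditional or marginal. Parts of sections 10.0 and 10.1 are redacted, so more detail may exist.

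**The concern.** In a logistic model with random effects, the product coefficient is a within-subject log odds ratio. Applying the inverse logit to a product mean with the random effects at zero gives the leakage probability of a typical subject. That is not the average over subjects, and when leakage is below 50% it is lower than the average.

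The plan therefore seems to mix three quantities: a conditional odds ratio that is tested, marginal proportions that are promised, and an estimated difference that can decide success under section 10.3. If typical-subject values were reported as marginal ones, both proportions and their difference would shrink. A new coupling that leaks more would then look closer to the current one, and the second route in section 10.3 would be easier to satisfy. In a trial meant to show that the new coupling is on par, that error would favour the new product.

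**Working it through.** **Inputs from the plan.** Binary leakage per bag change; fixed product and period effects; random subject and product-by-subject effects; two-sided 5% level; 40 completers; at least 6 bag changes per period. The one reproducible figure in the sample-size text is the number randomised, 40 / (1 − 0.20) = 50, which matches the plan. The present question does not depend on it.

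**Inputs assumed.** The visible text gives no leakage rates or variance components. Assumed logit-scale SDs are 0.5 to 2.0 for subject and 0.5 to 1.0 for product-by-subject. The total SD is s = √(subject SD² + interaction SD²), from √(0.25 + 0.25) = 0.71 to √(4 + 1) = 2.24.

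**Formulas.** With η the fixed-effect logit and Z standard normal:
- typical-subject probability = expit(η)
- marginal probability = E[expit(η + sZ)], by 80-point Gauss-Hermite integration.

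**Step 1: size of the error if typical-subject values were reported.** For each s, η was solved to give the stated marginal values.

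| s | true 10% v 20% shown as | difference (points) | model OR (marginal OR 2.25) | true 5% v 10%: difference (points) |
|---|---|---|---|---|
| 0.71 | 8.4% v 17.9% | 9.5 | 2.37 | 4.4 |
| 1.0 | 7.2% v 16.1% | 9.0 | 2.50 | 3.8 |
| 1.5 | 5.0% v 12.8% | 7.9 | 2.82 | 2.9 |
| 2.24 | 2.5% v 8.4% | 5.9 | 3.55 | 1.6 |

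The direction depends on the rate. At a true 50% there is no bias, and at 70% with s = 1 the back-transformed value is too high (73.5%).

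**Step 2: can the proportions be understated while the odds ratio also fails to match them?** Take a conditional odds ratio of 2, a typical-subject rate of 5% on the comparator, and s = 1.5.
- If typical-subject values are reported, they are 5.00% and 9.52%. Their odds ratio is (0.0952/0.9048) / (0.05/0.95) = 2.00, exactly the model's. Section 10.1's description holds, but the proportions are too low.
- If marginal values are reported, they are 10.06% and 16.22%. Nothing is understated. Their odds ratio is (0.1622/0.8378) / (0.1006/0.8994) = 1.73, so only the model odds ratio of 2 needs a label.

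The two faults are alternatives.

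**Step 3: is the test affected?** If the conditional odds ratio is 1, both products have the same η. With the same s, E[expit(η + sZ)] is then identical for both, so the marginal odds ratio is also 1. The integration gave exactly 1.000 at every s from 0 to 2.5. As a check, 400 trials were simulated under no difference (40 subjects, two products, 6 changes per period, subject SD 1.2, interaction SD 0.6) and analysed with a marginal model (GEE). It rejected in 5.75% of trials; the Monte Carlo standard error is √(0.05 × 0.95 / 400) = 1.1 points.

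**Step 4: would a wrong back-transformation be noticed?** In those simulations the mean observed leakage was 12.9%, while the typical-subject value was 7.6%. The by-product percentages that section 10.0 requires would put the first figure next to the second.

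**The case for a change.** The strongest contrary case is that the only explicit model specification is the random-effects one, so two competent analysts could follow section 10.0 and report different proportions and a different difference from the same data. For a primary endpoint that is undesirable, and at moderate heterogeneity the gap is not trivial: at s = 1.5, a 10-point difference would show as 7.9. Because section 10.3 accepts a difference judged not relevantly worse, shrinkage would help the new product.

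It stands that the derivation step is unstated and the odds ratio unlabelled. The rest does not carry. The harmful reading needs an analyst to report as marginal something that is not marginal, against the plan's own word and beside observed percentages that would expose it. The second route in section 10.3 has no numeric limit, so the visible text cannot show that any decision would change. The missing limit is a separate matter, and a more precise difference or a confidence interval would not supply it. Replacing the mixed model by GEE, or making a risk difference the primary quantity, is a choice on which statisticians reasonably differ; neither is needed to obtain marginal proportions.

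**Conclusion.** The concern does not call for a change. Followed as written, the plan reports marginal proportions, obtainable by averaging the fitted model over its random effects, and tests an odds ratio of 1, which is the same hypothesis on the conditional and marginal scales. That equivalence assumes a common random-effect variance for the two products, the natural reading of the single interaction term in section 10.0.

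The loss of 0.5 to 4.1 points from a true 10-point difference would arise only if typical-subject values were reported instead, with leakage below 50% and total logit SDs of 0.71 to 2.24, all of them assumptions. What is left is a gap in detail that a trial statistician fills in the ordinary course of programming and reporting: averaging over the random effects and labelling the odds ratio.

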10.1. Sample size

The primary objective is to investigate the performance of a new 2p coupling in comparison with the SenSura Mio Click coupling with regards to leakage at the coupling during wear in a clinical setting. This will be done by testing if the odds ratio for the estimated proportions of leakage with the two products is equal to one.

[REDACTED]

[REDACTED]

[REDACTED]

[REDACTED]

Drop-out subjects will not be replaced but to account for an assumed drop-out rate of 20%, 50 subjects will be randomized in the study.

10.2. Level of significance and power

A two-sided significant level of 5% will be applied. For a description of the power see section 10.2 above

10.3. Pass/fail criteria

The purpose of the investigation is fulfilled:

- if the estimated proportion of leakage from the new coupling system is not statistically significant different from the current SenSura Mio 2p Click solution,
- or the estimated difference is not clinically relevant worse.

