1.3. Other Vendors

The data management system is delivered by [REDACTED]. The system is designed for electronic data capture, and it is compliant with the requirements of 21 CFR part 11.

The subject will be required to download and install a Patient Cloud app onto their smart phone. See section 11 for further details.

The app will be used to record subject diary responses.

In case of emergency, please contact the Clinical Manager from the above list of sponsor representatives.

2. Justification for conducting the clinical investigation

People with intestinal stomas have, despite development of better stoma products, problems with leakage induced peristomal skin complications which influence quality of life negatively^{1,2}. Although, the primary cause of peristomal skin complications is leakage of ostomy effluents under the adhesive barrier^{3,4}, leakage could also occur from other parts of stoma devices, for example through the coupling in 2-piece stoma devices. Coloplast wants to apply a new coupling system with improved functionality for SenSura Mio users who use a 2-piece appliance. The justification for conducting this clinical investigation is to investigate that the new coupling system is on par with the existing coupling SenSura Mio Click system with regards to leakage at the coupling.

3. Objective(s) of the clinical investigation

The aim of the study is to investigate how a new two-piece (2p) coupling system is evaluated by users in comparison with SenSura Mio Click.

The primary objective is to demonstrate that the performance of the new 2p coupling system is comparable to SenSura Mio Click coupling with regards to leakage at the coupling during wear in a clinical setting.

The secondary objective is to evaluate product satisfaction and preference of the new two-piece (2p) coupling system by users in a clinical setting.

4. Investigational Products

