5.0. General

This investigation is an open-label, randomized, controlled, comparative, cross-over study with 2 test periods and 2 test sequences comparing a new 2p coupling system with SenSura Mio Click. Each test period is 21 days (± 2 days). Each subject will participate for a total of 42 days (± 4 days). The subjects will test the investigational product and the comparator in a 1:1 randomised order. A total of 50 subjects will be enrolled and

randomized to yield 40 subjects (assuming a 20% drop-out rate) who complete the study. The sample size calculation is based on at least 6 bag changes during each test period (≥ 2 changes per week).

If a potential subject is interested in participating after the first contact, a visit (visit 0) will be arranged.

The subject will receive both written and verbal information to ensure that the subject understands what was read and explained and can freely agree to participate in the investigation. During the visit, the Principal Investigator or designee will provide oral information about the investigation based on the Subject Information Form.

Before the test periods, the subjects are invited for a screening visit (V1). Subjects will be consented prior to any study procedures. Once consented, during their participation, the subjects will complete three study visits (V2, V3 and V4). The visits will be done remotely via video conference. A follow-up call will be scheduled 7 \pm 3 days after each test visit to ensure compliance with the provided product and study procedures. Additional calls may be scheduled if needed (assessed by the Principal Investigator or designee).

At every bag change the subject will be asked to complete a questionnaire via an app installed on their smartphone.

During the visits the subject will complete a questionnaire and discuss any adverse events or device deficiencies they may have had with the site personnel.

Coloplast will provide both the investigational product and the comparator product for all subjects.

If a subject experience a problem with the investigational product during the investigation, he/she should contact the investigator for advice. Subjects that cannot complete a test period with the test product may choose to use their own product (i.e., SenSura® Mio) for the remainder of the test period. However, this must be documented by the Principal Investigator.

[figure not shown]

Figure 1 Design of the investigation.

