8.0. Risk-benefit analysis of the investigational device

This clinical study is performed to confirm that the new coupling is on par with SenSura click with regards to leakage at the coupling.

A risk analysis according to ISO 14971 Application of risk management to medical devices has been conducted. Risks have been proven minimized or eliminated through appropriate design control, confirmed by pre-clinical bench, and laboratory testing.

The risk management process has been performed in accordance with the requirements stated in ISO 14971:2012 and in accordance with internal Coloplast procedures, including design verification, validated test methods, risk analysis and completion of a biological evaluation report for the test product.

To mitigate and reduce the risks, the site personnel will be trained, according to the IFU.

The investigation is conducted in accordance with current applicable standards. Please refer to section 15.0, Statement of compliance. The rights, safety and well-being of human subjects shall prevail over the interest of science.

Risks have been proven minimized or eliminated through appropriate design control, confirmed by pre-clinical bench, and laboratory studies.

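### The section 10.3 pass rule treats a non-significant difference, or a point estimate alone, as proof that the new coupling is comparable, so a leakier coupling can pass

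*Combined protocol and SAP*

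**What the plan says.** Section 3 gives the primary objective as to "demonstrate that the performance of the new 2p coupling system is comparable to SenSura Mio Click coupling with regards to leakage". Section 8.0 says the study is "performed to confirm that the new coupling is on par with SenSura click with regards to leakage at the coupling".

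The only primary test in the visible text is a test of no difference. In section 10.0, "it will be tested if the odds ratio is significantly different from 1 on a 5% test level". Section 10.1 describes "testing if the odds ratio for the estimated proportions of leakage with the two products is equal to one", and section 10.2 adds: "A two-sided significant level of 5% will be applied".

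Section 10.3 then sets the pass rule. The purpose is fulfilled if the new coupling's leakage proportion "is not statistically significant different from the current SenSura Mio 2p Click solution", "or the estimated difference is not clinically relevant worse". This section is not redacted. It gives no numeric margin and no confidence limit.

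On size, section 5.0 states: "The sample size calculation is based on at least 6 bag changes during each test period". It plans 50 randomized subjects to yield 40 completers. Parts of sections 10.0 and 10.1 are redacted, and section 10.2 refers to itself for the power.

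**The concern.** Showing that two products are comparable is a positive claim and needs evidence that rules out a relevant disadvantage. A non-significant test of an odds ratio of 1 does not supply it. The same result arises when the products are alike and when the data are too few to tell.

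The second condition does not repair this. Read naturally, it compares the point estimate with a threshold and ignores its uncertainty. Because the conditions are joined by *or*, it cannot take away a pass given by the first; it can only add passes. The trial therefore fails only when the result is both statistically significant and clinically relevantly worse.

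For a claim of parity, the error that matters is passing a coupling that leaks more. The rule does not control that error, and fewer completers or fewer recorded changes increase it. A pass would not support the objective in section 3.

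**Working it through.** **Inputs from the plan.** 40 completers and 50 randomized (sections 5.0, 6, 10.1); at least 6 changes per period (5.0), up to about 21 if changed daily (4.7); two-sided 5% test (10.2). The randomized number reproduces: 40 / (1 − 0.20) = 50. The 40 itself cannot be reproduced because its inputs are not visible.

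**Assumptions, not in the plan.** Comparator leak rates of 2, 5, 10 and 20% per change; subject SD 1.0 or 1.5 and product-by-subject SD 0.5 or 0.75 on the logit scale; an illustrative clinical threshold of 5 percentage points.

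**Step 1: hand check, treating changes as independent.** Each product has 40 × 6 = 240 changes. Power = Φ[(Δ − 1.96·SE₀)/SE₁], with SE₀ pooled and SE₁ unpooled, and the chance of meeting the first condition is 1 − power. Doubling the odds from 5% gives 9.5%:
- Δ = 0.0452, SE₀ = 0.0237, SE₁ = 0.0236
- power = 0.48, so the first condition is met with probability 0.52

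From 10% the doubled-odds rate is 18.2%, power is 0.73, and the probability is 0.27.

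**Step 2: simulation with within-subject correlation.** 10,000 trials per setting, 40 completers. The log odds ratio comes from an independence GEE with robust standard errors, a stand-in for the planned random-effects model. Ranges are over the four variance combinations. Chance of meeting the first condition:

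| Truth | Changes per period | 2% | 5% | 10% | 20% |
|---|---|---|---|---|---|
| Odds × 2 | 6 | 80–83% | 53–60% | 27–39% | 8–19% |
| Odds × 2 | 12 | 61–66% | 30–40% | 9–21% | 1–7% |
| Odds × 2 | 21 | 44–54% | 15–27% | 3–11% | 0–3% |
| Odds × 1.5 | 6 | 92–93% | 82–84% | 70–75% | 53–63% |

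With 30 completers, 6 changes and doubled odds, the figures rise to 86–89, 63–69, 41–50 and 18–32%. Truly equal products meet the condition in 92–98% of trials in every setting.

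On the absolute scale, doubled odds is an excess of 1.9, 4.5, 8.2 and 13.3 points at the four rates; odds × 1.5 is 1.0, 2.3, 4.3 and 7.3 points.

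**Step 3: whole rule against a 5-point threshold.** Pass = not significant, or estimated excess ≤ 5 points. Ranges are over all four leak rates and variance settings.

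| True excess | 6 changes | 12 changes | 21 changes | Upper 95% limit < 5 points |
|---|---|---|---|---|
| 5 points | 57–80% | 53–72% | 52–66% | 3–8% |
| 7.5 points | 17–61% | 10–48% | 6–37% | under 1% |
| 10 points | 3–41% | 1–24% | 0–16% | under 1% |

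The last two rows use a paired t test on subject-level proportions. At a true excess equal to the threshold, more data cannot bring the pass rate below about half, because the estimate falls below its own true value about half the time.

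**Step 4: what a confidence-limit rule needs.** For equal products, independent changes, a 5-point margin and 80% power, n = 2p(1 − p)(1.96 + 0.8416)² / 0.05²:
- p = 5%: 298.3, so 299 changes per product, or 299/40 ≈ 7.5 per completer
- p = 10%: 565.1, so 566 changes per product, or 566/40 ≈ 14 per completer

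With 240 changes, power is Φ(0.05/√[2p(1 − p)/240] − 1.96) = 71% at 5% leakage and 45% at 10%.

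**The case against.** Several counter-arguments have weight.

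- **Scale.** Five of the eight combinations of leak rate and odds ratio in Step 2 give an excess below 5 points, including every figure of 80% or more for 40 completers. A 5-point margin would not call those couplings unacceptable. This stands as a caution on reading the table. For truths beyond 5 points at 6 changes, the first condition is still met in 27–39% (odds × 2 at 10%), 8–19% (odds × 2 at 20%) and 53–63% (odds × 1.5 at 20%).
- **More data.** They do help once the true excess is beyond the threshold, as Step 3 shows. The floor of about one half applies only at the threshold.
- **A better coupling.** A significantly better product fails the first condition, and only the second lets it pass. That is a legitimate role, and a confidence-limit rule also serves it.
- **Redaction.** The hidden text may hold a clinically relevant difference, so it cannot be said that none was planned. It would not cure the rule: the first condition passes without it, and the second, as worded, applies it to the estimate.
- **Exploratory label.** Sections 6.5 and 10.0 call the study exploratory, and the synopsis and sections 5.6 and 10.1 speak only of investigating performance. That lowers the stakes, but section 10.3 still turns the result into a formal statement of success.
- **Blinded statistician.** Section 5.9 keeps the trial statistician blinded until database lock. This reduces the risk of a threshold chosen after seeing data but does not remove it, since the trial is open-label and the sponsor reviews data centrally during conduct (sections 9 and 11.1).

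**Conclusion.** The rule is wrong as written and must be changed. The defect follows from the wording of section 10.3 set against sections 3 and 8.0 and depends on no redacted figure.

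Its size does depend on assumed leak rates, variances and threshold, and on stand-ins for the planned model. Within those assumptions the risk is large when leakage is rare or changes are few. The first condition carries little risk when leakage is frequent and changes are daily: 0–3% at 20% leakage, 21 changes and doubled odds. At the threshold itself the whole rule passes at least about half of trials in every setting examined.

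**What to change.** Replace both conditions in section 10.3 with one: the purpose is fulfilled if the upper limit of the two-sided 95% confidence interval for test versus comparator leakage, as a marginal difference or an odds ratio, lies below a stated numeric margin. Choose the scale and write the number into section 10.3 before the first subject is enrolled. If the redacted text already holds a clinically relevant difference, state it there. Keep the test of an odds ratio of 1 only as a superiority test after non-inferiority has been shown. Check the sample size in sections 10.1 and 10.2 against this rule, and give the power for 40 completers with at least 6 changes per period.

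If no margin can be justified, or power is inadequate, delete the pass/fail claim, change *demonstrate* (section 3) and *confirm* (section 8.0) to *estimate*, and report the difference with its 95% interval. That fits the exploratory label.

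The cost is wording, one confidence limit from the planned model and a sample-size check. A pass becomes harder. For equal products and a 5-point margin, simulated power at 2, 5, 10 and 20% leakage is 93–94, 65–71, 39–47 and 23–29% with 6 changes, and 98–99, 83–90, 55–68 and 31–44% with 12. More recorded changes or more subjects may be needed. The simple interval simulated here was somewhat liberal at low leak rates (up to 8% against a nominal 2.5%), so the error rate of the interval from the planned model should be checked too.
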